5.10.4 Vital signs

Patients with clinically notable vital sign abnormalities will be listed and the corresponding values will be flagged in the listing.

Vital signs summaries using all available data

• For systolic BP, diastolic BP and pulse rate, shift tables using the high/normal/low/(high and low) classification defined in Table 5-2 will be produced to compare baseline to the worst post-baseline value by phase (core/extension).

Table 5-2 Clinically notable vital signs

Vital sign	High	Low
Systolic BP [mmHg]	≥ 160 with increase from baseline of ≥ 20	≤ 90 with decrease from baseline of ≥ 20
Diastolic BP [mmHg]	≥ 100 with increase from baseline of ≥ 15	≤ 50 with decrease from baseline of ≥ 15
Pulse rate [bpm]	≥ 120 with increase from baseline of ≥ 15	≤ 50 with decrease from baseline of ≥ 15

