Pasireotide's effect on QT prolongation was demonstrated by two thorough QT (TQT) studies [SOM230B2113] and [SOM230B2125]. The second TQT study [SOM230B2125] was designed to evaluate the effect of pasireotide on cardiac intervals using an individualized correction method to account for the known bradycardic effect of pasireotide. It was conducted as a follow-up to Study [SOM230B2113], which showed that pasireotide at the Maximum Tolerated Dose (MTD) of 1950 µg b.i.d dose induced prolongation of QTcF, whereas no relevant effect on QTcB was observed. The second TQT study confirmed an effect of pasireotide on QTcI of pasireotide at both the 600 µg bid and the 1950 µg bid dose. The maximal placebo-subtracted change from baseline in QTcI was seen at 2 hours post dose, at which time the mean (90% CI) difference was 13.19 ms (11.38; 15.01) for pasireotide 600 µg bid, and 16.12 ms (14.30; 17.95) for pasireotide 1950 µg b.i.d. Both pasireotide doses decreased heart rate, with a maximal difference to placebo observed at 1 hour for pasireotide

600 µg b.i.d (-10.39 bpm), and at 0.5 hours for pasireotide 1950 µg bid (-14.91 bpm). There were no subjects with QTcI or QTcF values that were increased more than 60 ms from baseline, or that exceeded 500 ms on Day 5, the last day of study treatment. Detailed information of the results of these two TQT studies can be found in the [Investigator's Brochure].

Pasireotide long acting release (LAR) formulation

A long acting formulation of pasireotide (pasireotide LAR) has been developed to reduce the number of injections from twice a day to once a month in order to enhance convenience and potentially provide a better efficacy profile with a smoother PK profile minimizing fluctuation from C_{max} and C_{min}.

Pasireotide LAR in healthy volunteers

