10.5.3.4 Other safety data

ECG

- shift table baseline to worst on-study treatment result
- listing of ECG evaluations for all patients with at least one abnormality

Vital signs

Definitions of notably abnormal results have to part of the MAP, CSP and/or RAP.

- shift table baseline to worst on-study treatment result
- listing of vital signs for all patients with at least one notably abnormal result

Gallbladder Ultrasound

Gallbladder data at each visit will be listed.

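### Vital-sign shift tables: Table 5-2 makes every baseline value Normal by construction, so only shifts out of Normal can appear and pre-existing abnormality is hidden

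*SAP*

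**What the plan says.** Protocol 10.5.3.4 (Other safety data) asks for two vital-sign outputs. One is a "shift table baseline to worst on-study treatment result"; the other is a listing of patients with at least one notably abnormal value. It leaves the definition of notably abnormal to other planning documents, including the RAP, which is this SAP.

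SAP 5.10.4 supplies the definition in Table 5-2 and uses it for the shift tables, by phase: "shift tables using the high/normal/low/(high and low) classification defined in Table 5-2 will be produced to compare baseline to the worst post-baseline value". The criteria are:

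- Systolic BP: High is "≥ 160 with increase from baseline of ≥ 20"; Low is "≤ 90 with decrease from baseline of ≥ 20".
- Diastolic BP: High is "≥ 100 with increase from baseline of ≥ 15"; Low is "≤ 50 with decrease from baseline of ≥ 15".
- Pulse rate: High is "≥ 120 with increase from baseline of ≥ 15"; Low has the same wording as diastolic Low.

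SAP 4.1.5 defines baseline as a single value, the most recent one before the first dose within a 28-day window. Neither document gives a separate rule for classifying a baseline vital sign.

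**The concern.** A shift table cross-classifies each patient's state at entry against the worst state on treatment. It needs a scale that can be applied to a single value at either time. Table 5-2 is not such a scale. It defines a notable change, and a baseline value has not changed from itself.

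The SAP's other safety sections avoid this. In SAP 5.10.2 the laboratory shift tables use CTCAE grades or low/normal/high classes, both of which can classify a baseline value. SAP 5.10.3 keeps ECG shift tables apart from the count of newly occurring abnormalities. Vital signs use one change-based rule for both purposes.

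At stake is how the tables are read. A reader who sees every patient in the Normal baseline row will conclude that nobody entered with abnormal blood pressure or pulse, and that every abnormality in the table arose on treatment. Neither conclusion follows. The listed exclusion criteria (Protocol 5.3) set no blood-pressure limit. Protocol 8.1.3 names hypotension and bradycardia among the adverse events of special interest, so these tables will be looked at.

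**Working it through.** There is no stated figure to reproduce. The check applies the rule to the values it is meant to classify.

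**Step 1: baseline.** Let b be the baseline value and v the value being classified. Systolic High requires v ≥ 160 and v − b ≥ 20. At baseline v = b, so v − b = 0 and the second condition fails for every b. The same holds for the other five categories, whose change conditions are 20 (systolic Low) or 15 (diastolic and pulse, High and Low). Enumerating whole-number values confirms it: 201 of 201 systolic values (60 to 260), 131 of 131 diastolic values (30 to 160) and 171 of 171 pulse values (30 to 200) classify as Normal. The ranges are assumptions; the result does not depend on them.

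**Step 2: cells that can be filled.** In the three-by-three High/Normal/Low grid, the only reachable cells are Normal to Normal, Normal to High and Normal to Low, that is 3 of 9 for each vital sign. Normal to (high and low) can also arise if a patient meets both criteria at different visits. With the change condition removed, all 9 cells are reachable for each vital sign.

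**Step 3: examples for systolic BP (mmHg).**

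| Baseline to worst | Change | Table 5-2 as written | Absolute limits only |
|---|---|---|---|
| 130 to 165 | +35 | Normal to High | Normal to High |
| 110 to 88 | −22 | Normal to Low | Normal to Low |
| 170 to 175 | +5 | Normal to Normal | High to High |
| 170 to 195 | +25 | Normal to High | High to High |
| 170 to 140 | −30 | Normal to Normal | High to Normal |
| 88 to 85 | −3 | Normal to Normal | Low to Low |
| 150 to 165 | +15 | Normal to Normal | Normal to High |

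The first two rows show that new notable changes are captured correctly as written. The next four are the problem: persistence and recovery disappear, and worsening from an abnormal start shares a cell with true new onset. The last row is not the baseline defect. It shows that the two rules answer different questions: one asks where the value lies, the other whether it moved far enough to be notable.

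**The case against.** The best defence is that the protocol leaves the definitions to the SAP, the SAP supplies them, and a limit-plus-change rule is a sensible way to find notable values on treatment. A programmer might also classify baseline by the absolute limit, since no change exists there, in which case only a sentence is missing. The rule is indeed suitable for newly notable values and should stay for that purpose. But the SAP text applies the whole of Table 5-2 to baseline. If the programming does something else, the SAP should say so.

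It can also be said that little rests on these tables. Clinically significant bradycardia is excluded at entry (Protocol 5.3), bradycardia and hypotension are covered by the special-interest adverse-event summaries, SAP Table 5-1 separately counts notable ECG heart rates, and SAP 5.1 provides for listing all data. This stands, and it limits the consequence. It does not make the tables' baseline row informative.

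Two stronger readings are tempting, and the documents support neither:

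- A reader might infer that the tables cannot show any shift. They can: Normal to High, Normal to Low and Normal to (high and low) all remain visible. Only the baseline margin is degenerate.
- A reader might set the 15 bpm fall required for Low pulse against the heart-rate effects in Protocol 1.2.1.2 (10.39 and 14.91 bpm below placebo) and infer that the table will miss the drug's effect. Those are group-mean differences at 1 hour and 0.5 hours in thorough QT studies of the s.c. formulation. Table 5-2 is applied to each patient's worst value over many visits on monthly LAR injections, so the means do not show how many individual falls stay below 15 bpm. That argument also concerns the choice of change threshold, not the classification of baseline.

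**Conclusion.** The point holds as a defect in the table's definition. As written, 100% of non-missing baseline values are Normal for all three vital signs in both phases. The tables therefore work as counts of newly notable values set out in shift-table form. They cannot separate new from pre-existing abnormality, nor show persistence or recovery.

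The number of patients affected cannot be calculated, because the documents give no baseline vital-sign distribution. It could be anywhere from none to all of the 33 randomised. The conclusion assumes that the SAP is programmed literally and that no document outside this set supplies a baseline rule.

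The consequence is limited to descriptive safety tables. The primary endpoint is unaffected, and baseline values can be recovered from the listings. If the flagged listing in SAP 5.10.4 uses the Table 5-2 criteria, it will not flag an abnormality that was present at entry and did not move by the required amount.

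**What to change.** In SAP 5.10.4, state that the shift tables classify both the baseline and the worst post-baseline value by Table 5-2's absolute limits alone: systolic BP ≥ 160 or ≤ 90 mmHg, diastolic BP ≥ 100 or ≤ 50 mmHg, pulse rate ≥ 120 or ≤ 50 bpm. A patient who crosses both limits after baseline goes to (high and low).

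Keep the limit-plus-change rule for counting, listing and flagging newly notable values. Both outputs are needed. On absolute limits, 170 to 195 mmHg becomes High to High, and its 25 mmHg rise is then visible only in the notable-value count.

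If baseline is already programmed on absolute limits, state that and confirm that the post-baseline value is classified on the same scale.

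The cost is one sentence and one changed derivation. The limits are already in the SAP, and no new data are needed.

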5.10.5 Gallbladder ultrasound

Gallbladder data at each visit will be listed.

5.11 Pharmacokinetics evaluation

Pharmacokinetic data were reported in [the 12 month CSR] and not applicable in the final analysis.

Page 19 CSOM230C1202

6 Interim analysis

No interim analysis was planned for this study which required considerations on multiplicity. However there are multiple analyses were performed with updated data. Please see Section 4.2 for further details.

7 Sample size calculation

The planned sample size of 30 was determined based on the accuracy of estimated total-group response rate at the end of 3 months of treatment.

The response rate is the proportion of responders, where responders are defined as patients with the reduction of mean GH levels to $< 2.5 \,\mu g/L$ and normalization of IGF-1. The response rates at 20 mg, 40mg and 60mg in Study SOM230C2110 were comparable (30% at 20mg, 41.7% at 40mg, and 38.5% at 60mg). Furthermore, the dose of pasireotide LAR will be adjusted according to efficacy and safety. It is considered, therefore, that the efficacy of pasireotide LAR can be evaluated more appropriately based on the response rate of all groups combined. In this study, based on the results from Study SOM230C2110, the expected total-group response rate will be at least 30%.

In Study SOM230C2305, patients inadequately controlled with 12 month octreotide LAR study treatment were crossed over to pasireotide LAR. The response rate at 3 months after crossover was 17.3% (two-sided 95% CI: [9.8%, 27.3%]). Since a large number of patients who enroll to this study are assumed to be inadequately controlled with octreotide LAR treatment, a clinically meaningful minimum response rate is set as 10% based on the lower limit of two-sided 95% CI, 9.8%.

The expected drop out rate is 10% based on the results from Study SOM230C2305. The patients with missing values of mean GH levels or IGF-1 at the assessment at 3 months of study treatment or who discontinue prior to the assessment at 3 months of study treatment will be considered as non-responders.

Under these assumptions, the expected total-group response rate adjusted by the expected drop out rate is 27%. The sample size of 30 can demonstrate that the lower limit of the Clopper-Pearson exact two-sided 90% CI for the total-group response rate is not less than the clinically meaningful response rate, 10%.

8 Changes from planned analysis in the protocol and Month 12 CSR

Comparing with the analysis for 12 months of study treatment CSR, the following analyses was added for final analysis (Table 8-1).

Table 8-1 List of changes from planned analysis

No.	Items	When	Note
1	Disposition table including patients who continue treatment beyond 24 months.	RAP for final CSR (See title page)	New
2	Concomitant medication by phase	RAP for final CSR (See title page)	New
3	Tumor volume by categorical longest diameter	RAP for final CSR (See title page)	New
4	Tumor volume listing with longest/shortest diameters	RAP for final CSR (See title page)	New
